1. SCIENTIFIC AIMS

The care of extremity trauma has evolved over the past 25 years. In the era of prolonged skeletal traction and/or casting following extremity trauma, the use of post-injury supervised physical therapy (PT) was required to achieve good outcomes. Seminal changes in the care of extremity trauma include early long bone fracture fixation and stable joint reconstruction. These techniques allow for immediate ambulation with assistive devices, early joint range of motion and major muscle group activation. However, evidence on the use of more efficient and cost effective rehabilitation methods has not evolved at the same pace. Consequently, post-injury, clinic-based PT is often uniformly included as a standard of care rehabilitation protocol for uncomplicated extremity fractures. *No data exist to guide clinical decision making regarding the necessity of this approach or to identify subgroups of patients who may be able to achieve similar outcomes using a standardized self-directed, home exercise program.* The impact of a home-based PT program on clinically relevant outcomes following isolated and uncomplicated lower extremity fracture has never been evaluated.

The purpose of this study is to compare the effectiveness and value of clinic-based PT and a home-based, self-directed exercise program (SDEP). The home exercise program will be developed by a team of physical therapists, orthopaedic trauma surgeons and experts in rehabilitation engagement in collaboration with patients recovering from traumatic lower-extremity injuries. The study will also determine which subgroups of individuals based on patient and injury characteristics are the best candidates for a home exercise program.

Hypothesis: The overall hypothesis is that return to work/major activities as well as clinical and functional outcomes and health-related quality of life for patients who receive clinic-based PT will be similar to patients receiving SDEP.

Specific Aim 1: To compare the effectiveness of SDEP, exercise instructions given by physician and clinic-based PT for improving return to work/major activities, clinical and functional/performance outcomes and health-related quality of life in patients following selected lower-extremity fractures.

Specific Aim 2: To determine which sub-groups of patients, based on patient and injury characteristics, are most likely to benefit from SDEP.

Specific Aim 3: To compare the cost-effectiveness of clinic-based PT and SDEP.

2. BACKGROUND & SIGNIFICANCE

There is little clinical debate that patients with multiple extremity injuries or injuries with associated complex soft tissue damage or nerve deficits benefit from supervised PT. Prior

research from the LEAP Study examined the impact of PT on patients with high energy trauma injuries below the distal femur.¹ While the surgeons and PTs differed in their assessment of perceived need for PT,^{2,3} evidence demonstrates the beneficial effect of PT for this patient population.⁴ Research on combat-related lower extremity limb salvage patients showed a significant benefit and a higher return-to-duty rate following intense and focused rehabilitation combined with an integrated orthotic.⁵⁻⁷ *However, the majority of lower extremity fractures seen in the military and civilian sectors are not combat related or of the severity of the LEAP limb salvage patients and, thus may not require intensive, clinic-based, supervised PT treatment.* Patients with isolated major lower extremity fractures may benefit from a self-guided, home-based post-injury exercise program. Studies evaluating home exercise programs for elective orthopaedic reconstruction surgery for joint replacement and ACL reconstruction have reported equivalent outcomes compared to in-person, supervised PT.⁸⁻¹² Because PT resources are critical, limited, and expensive in most civilian centers, identifying the patients who would most benefit from utilizing these resources could result in savings for both the patients and the health care systems, and lead to more efficient access to PT services by the population who needs them the most. In addition to health systems benefits, patients able to achieve positive outcomes through a home-based, self-directed exercise program would experience flexibility regarding when the exercises are performed.

PREVIOUS WORK DONE ON THE PROJECT

This study builds on a growing body of data that indicate, following various elective and traumatic orthopaedic procedures, patients who are provided structured self-directed home-based rehabilitation can achieve similar outcomes to those who receive traditional clinic based rehabilitation services.¹²⁻²³ Our institution recently completed an observational study assessing the outcomes of patients with severe ankle fractures with and without dislocation.¹² 47% of the patients (those in community based practice) received post-operative in-person, supervised PT, whereas 53% of the patients (those from an academic medical center) received only a surgeon directed home-based exercise program. At 6 months post injury, physical function outcomes measured by the Short Musculoskeletal Function Assessment (SMFA)²⁴ and Foot and Ankle Ability Measure (FAAM)²⁵ were similar. These data suggest that a structured, home-based exercise program is acceptable to patients and surgeons and that this may be an effective rehabilitation approach for post-fixation lower extremity fractures for selected injuries and in selected patients.

3. METHOD

We are proposing a pilot of a multi-center, randomized controlled trial that will compare clinic-based PT, self-directed, home exercise program (SDEP), and standard of care surgeon exercise instructions (SOC-SEI) in patients with selected lower-extremity fractures. Patients between the ages of 18-65 and with fractures of the femur or tibia treated with intramedullary fixation or with articular fractures of the distal femur (33A,B,C), proximal (41A,B,C) or distal tibia (43A, B,C) treated with plate fixation will be enrolled. Assessments will be conducted at baseline) and 3, 6, and 12 months after hospital discharge. Patients will complete a battery of questionnaires measuring psychosocial factors, return to major activities/work, pain, and health-related quality of life as well as performance-based tests with electronically augmented kinematic data capture via the Mobility Toolkit at each assessment visit. Range of motion and strength will also be

assessed using goniometry and a stabilized hand-held force gauge, respectively.

Inclusion criteria: Patients aged 18-65 with operative fractures of the femur and tibia (to include distal femur (33A, B), plateau (41A, B), pilon (43A, B), and selected ankle injuries (44A, B)) presenting to the Orthopaedic Surgeon for either acute care or for the follow-up of care performed elsewhere (within 14 days of the injury). All patients must be English or Spanish competent and able to be followed at the sites for at least 12 months following injury.

Exclusion criteria: Patients with ISS>18, bilateral lower-extremity injuries that preclude crutch ambulation, associated spine, pelvic, and/or acetabular fractures that otherwise alter weightbearing plans, type III B/C open fractures, Glasgow Coma Scale <15 at time of discharge, major peripheral nerve injury, or planned admission to a skilled nursing facility or inpatient rehabilitation facility, pregnant women, and patients diagnosed with a TBI will be excluded from the study.

Comparators: Patients will be randomized to one of three groups –

Insured patients

- **Clinic-based PT:** Patients will be referred to PT by the orthopaedic surgeon for enrollment into a clinic-based PT program per usual referral patterns at the surgeon's center. Patients will receive services based on their health care benefits defined by his or her insurance plan.
- **SDEP:** The full SDEP program, which will be developed by physical therapists, orthopaedic trauma surgeons, and investigators with experience in health behavior change, will be designed to maximize adherence/compliance with the program. The SDEP manual will provide detailed instructions on exercises, such as repetitions, frequency, and required equipment, which can be implemented in the home environment. The basis for the exercise regimen is derived from the AAOS sample home based exercise program available in handout form, which can be found at <http://orthoinfo.aaos.org/topic.cfm?topic=A00672>. The program provides instructions on exercises, repetitions or duration, frequency, and required equipment which can be implemented in the home environment.

Uninsured Patients

Patient with no access to health insurance will be approached for the study and randomized to the full SDEP program or standard of care/surgeon exercise instructions (SOC-SEI).

- **SDEP:** The full SDEP program, which will be developed by physical therapists, orthopaedic trauma surgeons, and investigators with experience in health behavior change, will be designed to maximize adherence/compliance with the program
- **Standard of Care-Surgeon Exercise Instructions (SOC-SEI):** stretching and range of motion instructions given by the treating surgeon or ACP.

Observational cohort

Patients who are unwilling to be randomized will be enrolled in an observational arm of the study. They will be asked to complete all baseline and follow-up assessments, and

participation in formal PT or SOC-SEI will be documented.

Data Collection: Patients will be assessed at baseline and then at 3, 6, and 12 months after hospital discharge. Demographic characteristics including co-morbidities, pre-injury health status and function, socioeconomic status, usual major activity prior to injury, education, and insurance status will be documented at the time of enrollment. Injury characteristics including associated injuries, hospital length of stay, and in-hospital complications will be collected. Fracture healing and weight-bearing status, as well as any complications, including readmissions and reoperations will be documented. Psychosocial characteristics that may impact outcomes (self-efficacy, patient activation, fear of movement/re-injury, resiliency, and depression) will be assessed at baseline and all follow-up visits.

Instrument	Baseline	3 months	6-months	12-months
Patient Characteristics	X			
Medical History	X			
Work Productivity and Activity Impairment Questionnaire (WPAI)	X	x	X	X
Paffenbarger Physical Activity Questionnaire	X	x	X	X
Pain Self-Efficacy Questionnaire (PSEQ)	X	x	X	X
Connor-Davidson Resilience Scale (CD-RISC)	X	x	X	X
Tampa Scale for Kinesiophobia (TSK)	X	x	X	X
Pain Catastrophizing Scale (PCS)	X	x	X	X
Veterans RAND 12 Item Health Survey (VR-12)	X	x	X	X
PROMIS Pain Interference Short Form		x	X	X
PROMIS Physical Function Short Form		x	X	X
PROMIS Global Health		x	X	X
Brief Pain Inventory (BPI)		x	X	X
Return to Usual Major Activity (RUMA)		x	X	X
Clinical Follow-up Form		x	X	X
Performance tests w/ IMU- at each clinic visit		x	x	x

Primary and Secondary Outcomes: The primary outcome measure for the study will be return to work/major activities. Secondary outcomes include the pain, functional status, health-related quality of life, physical activity, kinesiophobia, depression, psychosocial risk factors, time to recovery, range of motion assessed using a goniometer, and strength assessed using a stabilized hand held force gauge. Outcome measures covering multiple areas will be used to ensure that the potential benefits and/or limitations associated with selected interventions are effectively captured.

Secondary functional outcomes will be assessed with a battery of validated performance-based tests captured via the Mobility Toolkit (10m walk test, Timed Up and Go) at each clinic visit. The Mobility Toolkit is a HIPAA compliant, web-accessible, cloud-based application for

capturing performance tests in multiple clinics. It is built on a Microsoft Azure platform with custom MATLAB analytics. The mobility toolkit application currently allows us to gait test patients and compare their results over time (i.e. rehab trajectories) or compare results versus similar patients or matched non-injured controls. The data are captured by an Inertial Measurement Unit (IMU) that is chest-mounted, positioned at the top of the sternum using a simple harness (Figure 1). The IMU is a wireless-telemetry, 10 degree-of-freedom IMU which includes a tri-axial accelerometer, a tri-axial gyroscope, a tri-axial magnetometer and an onboard temperature sensor. Custom software has been developed to appropriately filter the raw data, establish a fixed global coordinate system (i.e. aligned with the body coordinate system), segregate gait segment data from turn data, and delineate and compile data for left and right strides for separate analyses. The software is also used to calculate quantitative descriptors of gait which are observable during subjective gait evaluation but not readily quantified. Set up and test time for the IMU is approximately 5 minutes and can be performed in almost any setting, including outpatient clinics.

Fig. 1 IMU with chest harness

4. Sample Size and Analysis Plan. The primary purpose of this study is to provide preliminary estimates of efficacy of the intervention and data supporting the feasibility of randomizing patients to two alternate types of rehabilitation services. Data will be used to determine the need for, and to power, a larger randomized trial of the intervention. The sample size of 60 patients per arm will allow us to calculate a confidence interval for the difference in mean PROMIS Physical Function scores between the two treatment groups assuming a common standard deviation of PROMIS Physical Function scores in the treatment groups of 17.

5. Potential Risk

There is a small risk of falling during the performance tests. These tests will be performed under close supervision by trained Research Coordinators using standard operating procedures.

Any time information is collected for a study, there is a small risk of breach of confidentiality. However, this risk is not greater than the risk that already exists in clinical settings when handling medical data.

6. Potential Benefits

The physical therapy intervention may or may not be better than the physical therapy program that would be prescribed to the participant outside of this study. In addition, study participants may experience satisfaction in knowing that the results of the study could help determine the best physical therapy program.

7. Data Management and Storage.

The Department of Orthopaedic Surgery utilizes the NIH-funded Research Electronic Data Capture (REDCap) project for all data management and storage. REDCap is a state of the art, metadata driven application for distributed data collection and data management in clinical studies.

Security. Privacy and security are central considerations for distributed data systems with access

to Personally Identifiable Information (PII). The overall private website will be secured with a challenge/response password protection mechanism. An additional level of security, requiring entry of a unique individual password, further protects access to the REDCap data management system. Numerous steps are being taken to maintain the integrity and security of the data system. First and foremost among these is the provision of careful training, certification, and guidance to all research staff. Each user account will have its own password and staff will be trained to recognize as misconduct the sharing of passwords.

Distributed Data System. The REDCap data management allows for a web-based, distributed data entry system using most web browsers to access an internet-connected database server. The system will permit research staff to have access to data as soon as they are entered, allowing for near-real-time recruitment reports and increased data entry availability and convenience for the clinical sites. The primary functions of the data system include the following existing features of the REDCap application: registration of all candidates for the trial; entry of all study data forms; inventory, management, and editing of study data; maintenance of full audit trails of all data entry and editing; and real time performance report generation. The REDCap data entry system also includes extensive data validation functionalities, including field level validation (i.e., checking the correct format and range of each entered item, intra-form validation, checking for logic errors, skip pattern violations across items on a form; and inter-form validation, checking for inconsistencies across forms).

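### The plan announces a three-group randomisation, but patients are randomised in two separate two-arm comparisons by insurance status, so PT versus SOC-SEI is not a randomised contrast and no analysis by insurance stratum is specified

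*Combined protocol and SAP*

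**What the plan says.** Specific Aim 1 is "To compare the effectiveness of SDEP, exercise instructions given by physician and clinic-based PT for improving return to work/major activities" and other outcomes. The opening of section 3 describes a "randomized controlled trial that will compare clinic-based PT, self-directed, home exercise program (SDEP), and standard of care surgeon exercise instructions (SOC-SEI"). The Comparators text then states "Patients will be randomized to one of three groups".

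The lists under that sentence are divided by insurance:

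- **Insured patients:** PT or SDEP. PT depends on coverage: "Patients will receive services based on their health care benefits defined by his or her insurance plan".
- **Uninsured patients:** "randomized to the full SDEP program or standard of care/surgeon exercise instructions (SOC-SEI"). PT is not offered.

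Insurance status is among the items recorded at enrolment (section 3, Data Collection). No stratified or insurance-adjusted analysis is described.

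Section 4 is the only text on sample size and analysis. It gives 60 patients per arm and a confidence interval for the difference in mean PROMIS Physical Function "between the two treatment groups assuming a common standard deviation of PROMIS Physical Function scores in the treatment groups of 17". It does not name the two groups, the stratum they come from, or whether SDEP patients from both strata count as one arm.

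**The concern.** A three-group randomised trial lets every pair of arms be compared on randomisation alone. This design does not. No patient can be allocated among three groups, and none can be allocated between PT and SOC-SEI. Yet Aim 1 lists all three interventions in one comparison, on the trial's primary outcome of return to work or major activities.

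An analyst who takes the three-group wording at face value could compare PT directly with SOC-SEI, or merge all SDEP patients into one arm and compare that arm with each of the others. Either step would credit treatment with any outcome difference between insured and uninsured patients. The study is meant to supply early efficacy estimates for planning a larger trial, so a confounded estimate could carry forward. The recruitment target is also unclear, because 60 per arm fits more than one layout.

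**Working it through.** **1. Which contrasts are randomised.** The arm lists give four cells:

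| | PT | SDEP | SOC-SEI |
|---|---|---|---|
| Insured | yes | yes | no |
| Uninsured | no | yes | yes |

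PT versus SDEP is randomised among insured patients, and SDEP versus SOC-SEI among uninsured patients. PT and SOC-SEI share no stratum, so a direct comparison has no overlap on which to adjust for insurance.

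**2. Size of the confounding.** Let D be the insured-minus-uninsured difference in mean outcome (or proportion) under the same treatment, and f the uninsured share of all SDEP patients. With no treatment effect and insured mean m:

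- PT mean = m
- SOC-SEI mean = m − D
- pooled SDEP mean = (1 − f)m + f(m − D) = m − fD

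The unadjusted differences are then:

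- PT − SOC-SEI = D
- PT − pooled SDEP = fD
- pooled SDEP − SOC-SEI = (1 − f)D

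The documents give neither D nor f. As an illustration, take D in percentage points of return to work:

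| Assumed D | PT vs SOC-SEI | PT vs pooled SDEP, f = 0.25 | f = 0.50 | f = 0.75 |
|---|---|---|---|---|
| 10 | 10 | 2.5 | 5 | 7.5 |
| 20 | 20 | 5 | 10 | 15 |
| 30 | 30 | 7.5 | 15 | 22.5 |

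**3. What adjustment can do.** A linear model with an insurance term and two treatment terms (SDEP as reference) has four parameters for four cell means. With no other covariates it therefore returns the two within-stratum contrasts exactly, and the pooling bias disappears. The PT versus SOC-SEI difference from that model is the sum of the two within-stratum contrasts, that is, an indirect estimate through SDEP. It assumes that treatment effects do not differ by insurance. All four cell means are already used, so the data cannot test that assumption.

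**4. Precision.** Section 4 gives 60 per arm and SD 17 but no target width or confidence level, so there is no stated width to reproduce. Taking 95% and the normal approximation, half-width = 1.96 × 17 × √(sum of 1/n over the cells used):

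- 60 versus 60: 1.96 × 17 × √(1/60 + 1/60) = 6.08 points
- 60 PT versus 30 insured SDEP: 1.96 × 17 × √(1/60 + 1/30) = 7.45 points
- indirect PT versus SOC-SEI, cells 60/30/30/60: 1.96 × 17 × √(1/60 + 1/30 + 1/30 + 1/60) = 10.54 points
- indirect, 60 in each of four cells: 1.96 × 17 × √(4/60) = 8.60 points

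**5. What 60 per arm could mean.** Two arms give 2 × 60 = 120 patients, three named arms 3 × 60 = 180, and four cells 4 × 60 = 240. If allocation is 1:1 within each stratum (an assumption; no ratio is given), 60 PT and 60 SOC-SEI patients bring 60 + 60 = 120 SDEP patients. Three arms of 60 then do not fit. The 30/30 split of SDEP would instead need 2:1 allocation in each stratum.

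**The case against.** The three-group sentence is a lead-in. The insured and uninsured lists follow it at once, so the split is disclosed, and three interventions do exist. Aim 1 does not itself use the word randomised. The purpose statement, the overall hypothesis and Aim 3 all concern PT versus SDEP, and the two groups in section 4 most naturally mean that pair. That contrast is properly randomised among insured patients. The study is a pilot.

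Most of this stands, and it limits the point. A reader might infer that the trial will produce a biased primary result. The documents do not support that: no passage says PT will be contrasted directly with SOC-SEI, or that SDEP will be pooled. A reader might also infer that every use of SDEP patients from both strata is confounded. That is too strong as well, because insurance status is recorded and SDEP is present in both strata, so stratification or adjustment removes the confounding. Nor do the documents establish how large an insurance gap would be, or that only 30 of 60 SDEP patients would be insured. With 1:1 allocation among insured patients, 60 PT implies 60 insured SDEP and the half-width stays at 6.1.

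What the objection does not answer is that the design statement and Aim 1 still name a three-way comparison, one pair of which has no randomised basis. Nothing in section 4 carries the insurance split into the analysis or says which contrast was sized.

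**Conclusion.** The point holds as a should-fix. The design is two parallel two-arm randomisations, and the wording of section 3 and Aim 1 does not match it. Both within-stratum contrasts are sound. PT versus SOC-SEI cannot be estimated by randomisation. Only an indirect estimate through SDEP is available, under an assumption the trial cannot check. SDEP pooled over insurance is confounded only if analysed without stratification or adjustment, which the plan neither states nor excludes.

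The structural finding rests on the arm lists alone. The sizes are illustrative: the bias is D for PT versus SOC-SEI and fD for PT versus unstratified SDEP, with D and f assumed. The widening from 6.1 to 7.5 PROMIS points applies only under the 60-versus-30 reading. The pilot purpose lowers the consequence but does not remove it, because the estimates are intended to inform a larger trial.

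**What to change.** - **Comparators and design statement (section 3):** replace the three-group sentence with two parallel randomised comparisons defined by insurance status at randomisation: PT versus SDEP in insured patients, and SDEP versus SOC-SEI in uninsured patients.
- **Aim 1:** reword it as those two contrasts.
- **Analysis (section 4):** estimate each contrast within its own insurance stratum. Require that any analysis combining SDEP across strata be stratified by or adjusted for insurance. State that PT versus SOC-SEI is not a randomised comparison, and label any indirect estimate through SDEP as exploratory, with its assumption given.
- **Sample size (section 4):** name the contrast to which 60 per arm refers, give the planned number in each of the four cells, and restate the confidence-interval width for those numbers.

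The cost is a change of wording and a short analysis paragraph. No extra patients are needed if precision is restated for the cells actually planned. The trial gives up a randomised three-way claim that it could not support, and the stated precision may turn out slightly wider.

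### No masking of outcome assessors is described and no limit on access to allocation is stated, so the examiner-measured secondary outcomes are open to expectation and encouragement bias

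*Combined protocol and SAP*

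**What the plan says.** The treatments are visibly different. In section 3 (Comparators), insured patients in the clinic arm are sent to in-person therapy: "Patients will be referred to PT by the orthopaedic surgeon for enrollment into a clinic-based PT program". The home-programme arm receives an exercise manual. Uninsured patients not given that programme receive "stretching and range of motion instructions given by the treating surgeon or ACP".

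The examiner-measured outcomes are all listed as secondary in section 3 (Primary and Secondary Outcomes). They are "range of motion assessed using a goniometer, and strength assessed using a stabilized hand held force gauge", together with the 10m walk test and Timed Up and Go. For the walk tests, "The data are captured by an Inertial Measurement Unit (IMU) that is chest-mounted", and custom software processes the signal.

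On who conducts the tests, the only statement is in section 5, in a paragraph about the risk of falling: "These tests will be performed under close supervision by trained Research Coordinators using standard operating procedures". No assessor is named for goniometry or the force gauge.

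On access, section 7 says "The system will permit research staff to have access to data as soon as they are entered". Each user has an individual password, but the section does not say which accounts can see the allocation or the programme forms.

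Neither blinding nor masking of anyone is mentioned anywhere in the document.

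**The concern.** Patients cannot be blinded to clinic therapy versus a home manual versus surgeon instructions, so any patient-reported outcome is unavoidably open-label. Examiner-measured function is different, because the person holding the goniometer or running the walk test could be kept unaware of the arm. The plan does not ask for this.

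These tests depend on effort. A patient's walking speed, force on the gauge and range at the joint can all respond to encouragement, and a goniometer is read by eye. The study hypothesis is that the arms will be similar, and section 2 already reports an observational study from the same institution pointing that way, so assessors may hold an expectation.

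The pilot is meant to give preliminary efficacy estimates and to inform a larger trial. A systematic shift does not shrink as the sample grows, and any examiner-measured estimate carried forward would carry the shift with it.

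**Working it through.** **Step 1. What the text settles and what it leaves open.**

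| Question | Section | What is stated |
|---|---|---|
| Can patients tell the arms apart? | 3, Comparators | Yes: clinic visits, a manual, or surgeon instructions |
| Who runs the performance tests? | 5 | Trained Research Coordinators, under standard procedures |
| Who measures range of motion and strength? | 3 | Not stated |
| Is any assessor masked? | none | Not stated |
| Who can see entered data? | 7 | Research staff, promptly |
| Is allocation hidden from anyone? | none | Not stated |
| How are the walk tests recorded? | 3 | By sensor and software |

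The text leaves the assessor's knowledge of the arm to chance and provides no barrier. It does not say that the assessor is unmasked.

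**Step 2. Precision available.** The plan gives 60 per arm and an SD of 17 for PROMIS Physical Function (section 4). It states no interval width, confidence level or power, so there is no figure to reproduce. Taking 95% as the level and two equal groups of 60, all measured:

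- On the PROMIS scale, for context: 1.96 × 17 × √(2/60) = 6.08 points.
- In SD units, which apply to any continuous outcome: 1.96 × √(2/60) = 1.96 × 0.1826 = 0.358 SD.

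**Step 3. An assumed bias against that precision.** The documents give no figure for assessor bias. I take a shift of 0.1 to 0.3 SD in favour of one arm purely as an illustration:

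- 0.1 / 0.358 = 28% of the half-width
- 0.2 / 0.358 = 56%
- 0.3 / 0.358 = 84%

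**Step 4. What the shift does when there is no true difference.** The chance that the 95% interval excludes zero in the favoured direction is Φ(b/√(2/60) − 1.96), where b is the bias in SD units:

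- b = 0: Φ(−1.96) = 2.5%
- b = 0.1: Φ(0.548 − 1.96) = about 8%
- b = 0.2: Φ(1.095 − 1.96) = about 19%
- b = 0.3: Φ(1.643 − 1.96) = about 38%

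A shift against a true difference would shrink the estimate by the same amount and make the arms look more alike. If fewer than 60 per arm attend the clinic tests, the interval widens and the bias becomes a smaller share of it, but the bias itself does not change.

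**The case against.** The strongest reply is that much is being read into silence, and several parts of that reply stand.

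- A reader might infer that coordinators are unmasked and that they take every physical measurement. The document says neither. The sentence in section 5 is a safety statement about the performance tests only, and the standard procedures it cites are not in the document.
- A reader might infer that coordinators can look up the arm. Section 7 grants access to research staff in general and links it to recruitment reports and data entry. It does not say that coordinators see allocation.
- A reader might infer that these are the only outcomes not taken from questionnaires. They are not. Section 3 (Data Collection) also says "Fracture healing and weight-bearing status, as well as any complications, including readmissions and reoperations will be documented".
- Instrumentation helps. The sensor and its software limit subjectivity in recording the walk tests, and the gauge is stabilized. What remains is mainly encouragement, effort and goniometer reading.
- All the affected measures are secondary. The primary outcome is return to work or major activities, and the sample-size statement rests on PROMIS Physical Function. Masking assessors protects neither if they are patient-reported.
- The 0.1 to 0.3 SD range has no source in the documents, and its lower end has a modest effect.

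These replies narrow the point but do not remove it. A protocol followed to the letter would let a coordinator who knows the arm test the patient, and nothing written would prevent or record that.

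**Conclusion.** The plan has a real gap that is cheap to close: it describes no assessor masking and no restriction on who sees allocation, while several secondary outcomes depend on the interaction between examiner and patient. This merits a change but does not threaten the primary outcome.

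The size of any bias is unknown. The 28% to 84% figure shows how sensitive the pilot would be under an assumed shift of 0.1 to 0.3 SD, a 95% level and 60 measured patients in each of two groups. It does not estimate what will happen. At 0.1 SD the effect is small. At 0.3 SD it is close to the smallest difference that the pilot can separate from zero.

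The documents also do not support some stronger remedies that a reader might draw from this point: hiring a separate assessor, dropping sites with a single coordinator from the main analysis, or hiding earlier test scores. Site staffing is not described, and section 3 presents comparison of a patient's results over time as a function of the toolkit.

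**What to change.** Add to section 3:

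1. Name the role that measures range of motion, strength and the performance tests. State that, where existing staffing allows, this is a coordinator who did not enrol or allocate the patient and is not told the arm.
2. Ask patients not to mention their programme before testing.
3. Record for each measurement whether the assessor was masked.

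Add to section 7: the REDCap account used for measurement cannot open the allocation field or the therapy and programme forms.

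Add to section 4: all measurements stay in the main analysis, and a sensitivity analysis compares results by masking status. Where masking was not possible, the report states this as a limitation.

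The cost is protocol wording, permission settings, one extra data item and one extra analysis. The downsides are some scheduling between existing coordinators and occasional accidental unmasking, which the recorded item would capture. Arms, visits and treatment do not change.
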